7.9.2 FVIII Inhibitors

Both a FVIII inhibitor screen and a quantitative FVIII Nijmegen-Bethesda inhibitor test will be performed at Addenbrooke's Hospital, UK. All inhibitor samples will be collected after a 3 day washout period, when it is anticipated that the pre-substitution FVIII level has reached a nadir¹².

FVIII inhibitor screening test

For the FVIII inhibitor screens, an APTT is performed on a 50/50 mix of a subject's plasma and normal pooled plasma, and compared with the APTT for the subject's plasma and that of normal pooled plasma. A positive inhibitor screen is defined as one that does not correct the APTT by > 50% of the difference between the subject's value and the normal pooled plasma value. To rule out the presence of a time-dependent inhibitor, 50/50 mixes of the subject's plasma and normal plasma are compared following incubation together or separately for 2 hours at 37°C. Time-dependent inhibition is defined as > 4 seconds' prolongation of the incubated mixture relative to the plasmas incubated separately.

FVIII Nijmegen-Bethesda inhibitor test

A Nijmegen-Bethesda assay will also be performed using the same sample as above. A result of ≥ 0.6 BU confirms that the subject has developed inhibitors to FVIII. If this occurs, the test will be repeated on a separate sample; if both tests are confirmed to be ≥ 0.6 BU this will be reported by

the Investigator as an SAE (see Appendix I). The Central Laboratory will notify both the Contract Research Organisation (CRO) and Sponsor immediately if any sample has a value of ≥ 0.6 BU, even if the repeat analysis has not been conducted.

If there is a discrepancy between the FVIII inhibitor screen and Nijmegen-Bethesda assay result, analyses will be repeated on reserve samples and, if necessary, additional samples from the subject, until an unequivocal result, or a reason for the discrepancy, is obtained.

If necessary, repeat FVIII inhibitor quantitative assays will be performed on reserve samples from earlier timepoints, in an attempt to identify the point at which an immune response was initiated. The subject's progress will be monitored closely and if any additional FVIII inhibitor samples are required, these should be taken in triplicate to allow repeat testing and assessment of possible 'transient' inhibitors.

If required, additional methodologies may be used to detect and quantitate inhibitors to FVIII. Any such methodologies will be described in detail in the clinical study report.

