8.1.1 Primary Efficacy Variable

The primary efficacy variable is assessment of the immunogenicity of Optivate[®] by monitoring plasma inhibitor levels for at least 100 EDs for each subject.

Factor VIII inhibitor screens and Nijmegen-Bethesda assays

Pre-bolus blood samples for FVIII inhibitor screens and quantitative assays will be collected at the Screening Visit, Baseline Visit (V1), V2, V3 and the End-of-Study Visit (V4), and at any unscheduled Visit conducted because of excessive bleeding or following an emergency bleed.

In accordance with the CHMP guidelines, results from a recovery assessment will also be required to confirm an inhibitor¹², in addition to the inhibitor test (see Section 7.7.2).

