10.6.1 Primary Endpoint

The primary efficacy endpoint is to assess immunogenicity of Optivate[®] by monitoring plasma inhibitor level for at least 100 EDs for each subject.

FVIII inhibitor evaluation

FVIII inhibitor screen data will be listed. FVIII quantitative inhibitor results will be listed. Shift tables will present the number of subjects with positive (≥ 0.6 BU) and negative (< 0.6 BU) results and those for whom the results change during the study. The number of exposure days until development of inhibitors will be summarised.

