7. GENERAL ASPECTS FOR STATISTICAL ANALYSIS

7.1. GENERAL METHODS

Statistical outputs will be generated using SAS version 9.3 (or later).

The study only has one treatment and so all summary tables will have a single results column for Optivate[®]. However, if subjects suffering from severe haemophilia A with basal FVIII values of < 2% rather than < 1% are recruited into the study, an additional two results columns will be presented, one for subjects with a basal FVIII < 1%, and one for subjects with a basal FVIII $\ge 1\%$ (see Section 6.3).

Continuous variables will be summarised using the number of observations (n), mean, 95% confidence interval for the mean, standard deviation (SD), median, minimum, and maximum. Minima and maxima will be quoted to the number of decimal places as recorded in the CRF, means and medians will be quoted to one further decimal place, and SDs will be quoted to one further decimal place than the mean value. Categorical variables will be summarised using number of observations (n), frequency and percentages of subjects. Percentages will be rounded to one decimal place, with the exception of 0% and 100%, which will be presented to no decimal places.

All relevant subject data will be included in listings. All subjects entered into the database will be included in subject data listings.

Data from unscheduled visits will not be included in the summary tables. These data will be listed only.

Where multiple data/results are available at a given visit for the same parameter, the first non-missing result will be used in the summary tables. All data will however be listed.

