9. EFFICACY

9.1. PRIMARY EFFICACY ENDPOINT AND ANALYSIS

The primary efficacy endpoint is the assessment of immunogenicity of Optivate® by monitoring plasma inhibitor levels for at least 100 EDs for each subject.

Pre-bolus blood samples for quantitative assays will be collected at the Screening Visit, Baseline Visit (Visit 1), Visit 2, Visit 3, the End of Study Visit (Visit 4) and possibly also at unscheduled visits if deemed necessary.

Inhibitor screen data will be listed only.

Quantitative inhibitor results will be listed.

Summaries of quantitative inhibitor levels will be based on both the Per Protocol and Safety populations.

At each visit, the number and percentage of subjects with positive (\geq 0.6 Bethesda Units) and negative (< 0.6 Bethesda Units) results will be summarised.

Shift tables cross tabulating positive/negative status (based on the Bethesda assay) at the Baseline Visit against those at Visits 2, 3 and 4 will be presented. Shifts from the Baseline Visit to any unscheduled visits will also be summarized. Note, should a subject have more than one unscheduled visit then the worst case assessment (positive) will be used in the summary.

The number of exposure days until development of inhibitors (positive status) will be summarized.

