12. CHANGE FROM ANALYSIS PLANNED IN PROTOCOL

There are no changes to the analyses planned in the protocol.

Sponsor: BPL

Protocol: 8VWF07

Version: 1.0

Statistical Analysis Plan

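### SAP 9.1 counts any single result of 0.6 BU or more as inhibitor development, although the protocol calls for a repeat sample and a recovery result to confirm one

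*SAP*

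**What the plan says.** Four sections bear on what counts as the primary event.

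- **SAP 9.1** sets positive at 0.6 BU or more, bases the shift tables on the Bethesda assay, and adds: "The number of exposure days until development of inhibitors (positive status) will be summarized". The bracketed words equate development of an inhibitor with a positive assay result.
- **Protocol 10.6.1** uses the same cut-off for its shift tables. Its exposure-day sentence has no bracket: "The number of exposure days until development of inhibitors will be summarised". The event is not defined there.
- **Protocol 8.1.1**, which describes the primary variable, says that, in addition to the inhibitor test, "results from a recovery assessment will also be required to confirm an inhibitor". It gives no recovery cut-off.
- **Protocol 7.9.2** says that a result of 0.6 BU or more "confirms that the subject has developed inhibitors to FVIII. If this occurs, the test will be repeated on a separate sample". The SAE report depends on both results being 0.6 BU or more. If the inhibitor screen and the Bethesda assay disagree, analyses are repeated "until an unequivocal result, or a reason for the discrepancy, is obtained".

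Three SAP rules decide which result reaches a table. Under SAP 7.1, when a visit has several results for a parameter, "the first non-missing result will be used in the summary tables". The same section says: "Data from unscheduled visits will not be included in the summary tables". SAP 9.1 nevertheless summarises shifts from baseline to unscheduled visits, taking the worst case (positive) when a subject has more than one.

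SAP 12 states: "There are no changes to the analyses planned in the protocol".

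**The concern.** The documents hold three criteria that are not equivalent: one positive assay, a positive assay plus a positive repeat, and a positive assay plus a recovery result. The SAP tables apply only the first. Protocol 7.9.2 does not settle the matter, because it calls one result confirmatory and then asks for a second. It does not say what a negative repeat does to the first result.

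This is the primary objective in a study of 10 evaluable subjects, so the classification of one subject is the whole result. If the definition is still open when a positive appears, it will be chosen with that case in view. The primary tables and the SAE tables could also disagree. A first positive with a negative repeat would count as inhibitor development under SAP 9.1 but would not meet the two-sample SAE rule in Protocol 7.9.2.

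**Working it through.** The plan has no power or sample-size figure to reproduce: Protocol 10.8 says that 10 evaluable subjects were agreed with the regulator. The check follows one case through the SAP's rules and then sizes its effect.

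**Step 1. Follow a first result of 0.6 BU or more whose repeat is below 0.6 BU.**

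| Where the results fall | Rule that applies | What is tabulated |
|---|---|---|
| Both recorded under the same visit | SAP 7.1, first non-missing | Positive; the repeat is not used |
| First at a scheduled visit, repeat at one unscheduled visit | Each visit shown separately | Scheduled visit positive; unscheduled shift negative |
| First and repeat at two unscheduled visits | SAP 9.1, worst case | Positive |

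Protocol 7.7.2 lists repeat samples among the reasons for an unscheduled visit, so the second and third rows are realistic. On every route the first positive stays in a primary table. The exposure-day summary has no repeat rule of its own. Because it is tied to positive status, it would count this subject as well.

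**Step 2. Ask what the recovery result does.** It enters none of these rows. SAP 9.2 analyses recovery only as a secondary endpoint.

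**Step 3. Ask what a discrepancy between screen and Bethesda assay does.** SAP 9.1 lists screen data only and gives no rule for the resolved result. If the re-analysis is recorded under the same visit, SAP 7.1 keeps the first Bethesda value, whichever way it points.

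**Step 4. Size one reclassified subject.** Exact (Clopper-Pearson) 95% limits for x of n:

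- x = 0: lower 0; upper 1 − 0.025^(1/n)
- x = 1: lower 1 − 0.975^(1/n); upper the 0.975 quantile of Beta(2, n − 1)

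Inputs: n = 10 (evaluable subjects, Protocol 10.8) and n = 12 (planned enrolment, taken as the Safety Population if all are treated and have results).

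- 0/10: upper = 1 − 0.025^(1/10) = 1 − 0.6915 = 30.8%
- 1/10: lower = 1 − 0.975^(1/10) = 0.3%; upper = 44.5%
- 0/12: upper = 1 − 0.025^(1/12) = 1 − 0.7354 = 26.5%
- 1/12: lower = 0.2%; upper = 38.5%

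One unconfirmed result therefore moves the point estimate from 0% to 10.0% (Per Protocol) or 8.3% (Safety), and the upper limit by 13.7 points (44.5 − 30.8) or 12.0 points (38.5 − 26.5). No assay error rate enters, because the documents give none.

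**The case against.** The strongest reply is that the SAP follows the protocol's own analysis section. Protocol 10.6.1 plans listings, shift tables at 0.6 BU and an exposure-day summary, and names no confirmation step. Protocol 7.9.2 is a laboratory procedure. In a safety study, tabulating every positive errs on the cautious side. Protocol section 2 reports no inhibitors in 130 patient-years in the two earlier studies in previously treated patients, so the rule may never operate.

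Much of this stands, and it rules out several stronger readings that a reader might infer.

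- *That the SAP does not say which result is tabulated.* It does, for several results at one visit and for several unscheduled visits. The difficulty is that those rules bypass confirmation.
- *That both documents equate a positive result with inhibitor development.* Only SAP 9.1 does; Protocol 10.6.1 leaves the event undefined.
- *That SAP 12 is plainly false.* Set against Protocol 10.6.1 it is defensible. Set against Protocol 8.1.1 it leaves the dropped recovery requirement unexplained.
- *That a subject who develops an inhibitor and stops before 100 EDs disappears.* Such a subject leaves the Per Protocol Population, but SAP 9.1 and the table index plan every inhibitor table for the Safety Population too, and SAP 7.4 places withdrawal data under End of Study. Two-sample cases also surface as SAEs.
- *That SAP 7.1 and 9.1 contradict each other on unscheduled visits.* SAP 9.1 can be read as a specific exception; the SAP simply does not say so.

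What the reply does not answer is Protocol 8.1.1. It sits in the definition of the primary variable, requires recovery data for confirmation, and has no counterpart in the SAP. Caution is a reason to show every positive, not to label each one as inhibitor development.

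**Conclusion.** The point holds and should be fixed before database lock. Followed exactly, SAP 9.1 would report a positive with a negative repeat, or with no supporting recovery result, as inhibitor development in the primary exposure-day summary. This is a stated rule that departs from the confirmation steps in Protocol 7.9.2 and 8.1.1, not merely missing detail.

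For a first positive that is not borne out, the error runs toward over-counting. Listing 18 carries all inhibitor samples, so a reader could reclassify the case by hand.

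The size rests on full data in each population and exactly one unconfirmed positive; if no positive occurs, the definitions agree. The table mock-ups are an attachment that was not available and may settle some layout points. Neither the SAP text nor the table index has a row for a confirmed inhibitor at any time.

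**What to change.** Before database lock:

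1. Reconcile Protocol 7.9.2, 8.1.1 and 10.6.1 and SAP 9.1 into one analysis definition of a confirmed inhibitor. The sponsor should state how the repeat sample and the recovery result enter it, including a missing recovery result, consistently with the two-sample SAE rule. Neither document states that repeat and recovery are jointly required, and neither gives a recovery criterion, so this review does not supply either.
2. Base the exposure-day summary on that definition and state which sample dates the event.
3. Add one row to the SAP 9.1 tables: n/N with a confirmed inhibitor at any time after the first Optivate dose, with an exact 95% CI, for the Per Protocol and Safety Populations. Add a separate line for positives not confirmed.
4. Keep the per-visit tables of all results of 0.6 BU or more. State which Bethesda result stands after a discrepancy with the screen, and that the unscheduled-visit shift summary is an exception to SAP 7.1.
5. Record any departure from the protocol in SAP 12.

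The cost is wording in both documents, one derived variable, two table lines and one sponsor decision. No new sampling is needed: the repeat is already ordered, and recovery is already assessed at each visit and when an inhibitor is suspected (Protocol 4.2, 4.2.1 and 7.7.2). The downside is a visibly wide interval, which is a fair picture of what 10 subjects can show.

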4.3. DETERMINATION OF SAMPLE SIZE

No formal sample size calculation was performed, as no formal hypothesis testing is planned. The sample size of 10 evaluable subjects was agreed with the German regulatory authority as part of the licensing agreement for Optivate[®]. Therefore for this study 12 subjects will be enrolled to ensure data for 10 evaluable subjects.

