7.3. MISSING DATA

All available data will be used in the statistical analysis. There will be no imputation for missing data.

Sponsor: BPL

Protocol: 8VWF07

Version: 1.0

Statistical Analysis Plan

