16. INDEX OF TABLES

- Table 14.1.1 Subject Disposition, All Screened Subjects
- Table 14.1.2 Study Duration, Safety Population
- Table 14.1.3 Demographics and Baseline Characteristics, Safety Population
- Table 14.1.4 Medical History, Safety Population
- Table 14.1.5.1 Prior Medications, Safety Population
- Table 14.1.5.2 Concomitant Medications, Safety Population
- Table 14.2.1.1 FVIII Inhibitor Status, Per Protocol Population
- Table 14.2.1.2 FVIII Inhibitor Status, Safety Population
- Table 14.2.1.3 Shifts in FVIII Inhibitor Status, Per Protocol Population
- Table 14.2.1.4 Shifts in FVIII Inhibitor Status, Safety Population
- Table 14.2.1.5 Number of Exposure Days Until the Development of Inhibitors (Positive Status), Per Protocol Population
- Table 14.2.1.6 Number of Exposure Days Until the Development of Inhibitors (Positive Status), Safety Population
- Table 14.2.2.1 Recovery of Current Factor VIII and First Dose of Optivate, Per Protocol Population
- Table 14.2.2.2 Recovery of Current Factor VIII and First Dose of Optivate, Safety Population
- Table 14.2.3.1 Optivate Recovery (IU/dL per IU/kg) by Visit, Per Protocol Population
- Table 14.2.3.2 Optivate Recovery (IU/dL per IU/kg) by Visit, Safety Population
- Table 14.2.3.3 Optivate Recovery (IU/dL per IU/kg) by Batch, Per Protocol Population
- Table 14.2.3.4 Optivate Recovery (IU/dL per IU/kg) by Batch, Safety Population
- Table 14.2.3.5 Optivate Recovery (IU/dL per IU/kg) by Subject, Safety Population
- Table 14.2.4.1 Bleeds by Subject, Per Protocol Population
- Table 14.2.4.2 Bleeds, Per Protocol Population
- Table 14.2.4.3 Bleeds by Subject, Safety Population
- Table 14.2.4.4 Bleeds, Safety Population
- Table 14.2.5.1 Investigator's Assessment of Effectiveness of Optivate, Per Protocol Population
- Table 14.2.5.2 Investigator's Assessment of Effectiveness of Optivate, Safety Population
- Table 14.2.6.1 Subject's Assessment of Effectiveness of Optivate ,Per Protocol Population
- Table 14.2.6.2 Subject's Assessment of Effectiveness of Optivate, Safety Population
- Table 14.2.7.1 Optivate Exposure Days, Per Protocol Population
- Table 14.2.7.2 Optivate Exposure Days, Safety Population
- Table 14.2.7.3 Total Optivate Dose, Per Protocol Population
- Table 14.2.7.4 Total Optivate Dose, Safety Population
- Table 14.2.7.5 Total Optivate Infusions, Per Protocol Population
- Table 14.2.7.6 Total Optivate Infusions, Safety Population
- Table 14.2.7.7 Optivate Dose per Infusion, Per Protocol Population

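### The planned summary of exposure days to inhibitor development covers cases only, and no output described in the SAP text relates inhibitors to exposure days at risk or bounds the risk

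*SAP*

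**What the plan says.** The primary endpoint is immunogenicity, followed through inhibitor tests over at least 100 EDs per subject. SAP 9.1 plans three kinds of summary, each in the Per Protocol and Safety Populations:

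- Status by visit: "At each visit, the number and percentage of subjects with positive" and negative results, with the cut at 0.6 Bethesda Units (BU).
- Shift tables from Baseline to Visits 2, 3 and 4, and to unscheduled visits.
- Time to inhibitor: "The number of exposure days until development of inhibitors (positive status) will be summarized". Protocol 10.6.1 is no more specific: "The number of exposure days until development of inhibitors will be summarised".

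The last item has two tables in SAP 16: "Table 14.2.1.5 Number of Exposure Days Until the Development of Inhibitors (Positive Status), Per Protocol Population" and, as Table 14.2.1.6, "Number of Exposure Days Until the Development of Inhibitors (Positive Status), Safety Population". No method is attached to either. The only general rule that could apply is in SAP 7.1: "Continuous variables will be summarised using the number of observations (n), mean, 95% confidence interval for the mean", then SD, median, minimum and maximum. Categorical summaries under the same section are counts and percentages, without an interval.

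On size, SAP 4.3 says: "Therefore for this study 12 subjects will be enrolled to ensure data for 10 evaluable subjects". SAP 6.1 limits the Per Protocol Population to subjects with at least 100 EDs. SAP 4.1 names inhibitor development as an example of an adverse event that may end a subject's treatment. SAP 9.2.4 summarises EDs per subject as a separate item.

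**The concern.** EDs until an inhibitor appears is a time-to-event quantity. It has a value for a subject who turns positive and none for a subject who does not. Without a rule that credits a negative subject with the EDs observed up to the last negative test, the summary can be computed only among cases. It then describes when inhibitors were found, given that they were found. It does not describe how often they arise per unit of exposure.

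The objective is framed in EDs, and a small study with few or no cases has one main quantitative message: how large a risk the observed exposure still allows. A blank table, or a single number with no spread, does not carry that message. The Per Protocol version has a further weakness. A subject withdrawn because of an inhibitor before 100 EDs is outside that population, so the table can lose the kind of case it exists to describe.

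**Working it through.** **Inputs.** 10 evaluable and 12 enrolled subjects (SAP 4.3); at least 100 EDs per evaluable subject (SAP 6.1); no inhibitors in two earlier studies, with 8,157 EDs reported for their follow-up period (Protocol 2). The plan gives no assumed inhibitor risk, power or precision, so there is no figure of its own to reproduce. The risks below are assumptions, shown as a range.

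**Step 1: what the tables would hold.** With risk p per subject over 100 EDs and n independent subjects, P(no case) = (1 − p)^n and P(one case) = n·p·(1 − p)^(n−1). At least two cases are needed for an SD or an interval for the mean.

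| Assumed p | No case, n = 10 / 12 | One case, n = 10 / 12 | Two or more, n = 10 / 12 |
|---|---|---|---|
| 0.1% | 99.0% / 98.8% | 1.0% / 1.2% | <0.1% / <0.1% |
| 1% | 90.4% / 88.6% | 9.1% / 10.7% | 0.4% / 0.6% |
| 2% | 81.7% / 78.5% | 16.7% / 19.2% | 1.6% / 2.3% |
| 5% | 59.9% / 54.0% | 31.5% / 34.1% | 8.6% / 11.8% |
| 10% | 34.9% / 28.2% | 38.7% / 37.7% | 26.4% / 34.1% |

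The n = 10 column flatters the Per Protocol table, because it ignores cases removed by the 100-ED requirement.

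**Step 2: which risks fit the earlier data.** For zero events the two-sided 95% upper limit on the expected count is −ln(0.025) = 3.689. Over 8,157 EDs that is 3.689 / 8.157 = 0.45 per 1,000 EDs. With a constant rate, the risk over 100 EDs is 1 − exp(−0.0452) = 4.4%. Even at that limit, P(no case) is exp(−0.452) = 63.6% for 10 subjects and exp(−0.543) = 58.1% for 12. An empty table is the more likely result up to p = 1 − 0.5^(1/10) = 6.7% for 10 subjects, or 1 − 0.5^(1/12) = 5.6% for 12.

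**Step 3: what a denominator would add after zero cases.** Assume each subject contributes exactly 100 EDs.

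- Subjects: the exact (Clopper-Pearson) upper limit is 1 − 0.025^(1/n). For 0/10 it is 30.8%; for 0/12 it is 26.5%.
- Exposure: the exact Poisson upper limit is 3.689 / EDs. For 10 × 100 = 1,000 EDs it is 3.69 per 1,000; for 1,200 EDs it is 3.07 per 1,000.

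**Step 4: what it would add after one case.** Suppose 10 subjects, one of them first positive at 12 EDs (illustrative). The planned statistics give a mean of 12 EDs with n = 1 and no SD or interval. EDs at risk are 12 + 9 × 100 = 912, so the rate is 1 / 912 = 1.10 per 1,000 EDs (95% CI 0.03 to 6.11), and 1/10 has an exact interval of 0.3% to 44.5%. Detection at 62 EDs gives 1 / 962 = 1.04 per 1,000, and at 100 EDs 1.00, so the rate hardly depends on when the case is found.

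**Step 5: how precisely onset is known.** Scheduled on-treatment tests after V1 fall at 10–15, 50–75 and at least 100 EDs (SAP 4.6). A first positive at Visit 3 places onset in a gap of 50 − 15 = 35 to 75 − 10 = 65 EDs. A mean or a smooth curve of onset would suggest more precision than the tests give.

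**The case against.** Much of the case against acting is sound, and it limits the point.

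A reader might infer that the planned table looks the same whatever the number exposed. It does not: SAP 14.2.4 puts the population size N in the column heading, distinct from n, so one case in 12 can be read off directly.

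A reader might also infer that inhibitor-free subjects are absent from the primary analysis. They are not. The per-visit and shift tables count them in both populations, and visits are tied to minimum ED counts. Early leavers appear under End of Study in Safety Population summaries (SAP 7.4). EDs are summarised in Tables 14.2.7.1 and 14.2.7.2 and listed by subject in Listing 29. With zero cases, total EDs are close to EDs at risk.

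SAP 7.3 is not evidence either way. "There will be no imputation for missing data" concerns missing values, and remaining inhibitor-free is an outcome, not a missing value. Nor do the documents say that the sponsor expects no inhibitors; they report earlier results only.

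That the SAP 7.1 statistics for continuous variables would be used is an inference. SAP 9.1 names no statistics, and the mock-ups (SAP 19.1) are an attachment that was not available. They could show another layout, though the SAP text points to none.

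The study is descriptive, its size was agreed with the regulator, and onset time among cases is a legitimate item to report.

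What remains is narrower. The visit tables carry no EDs and no interval. The End of Study row pools early leavers whatever their exposure. The ED tables are not linked to inhibitor status. Inhibitors would also appear among serious adverse events, but again only as counts and percentages.

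**Conclusion.** The point holds as a specification gap of modest weight that is worth closing. As written, the time-to-inhibitor tables can describe cases only. An empty table or a single value has a combined probability of at least 88% for any assumed risk up to 5%, and an empty table alone is the more likely result at every constant rate compatible with the earlier 8,157 EDs. No output described in the SAP text relates inhibitor events to EDs at risk or states an upper limit on risk, and the Per Protocol version can omit a case withdrawn before 100 EDs. The documents do not support saying that exposure data are lost or that the primary endpoint goes unreported: a zero-case result can be read from the status tables, and the EDs can be recovered.

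This rests on independent subjects, 10 to 12 of them with about 100 EDs each, a constant rate when the earlier data are carried over, and the SAP text without its mock-ups.

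**What to change.** In SAP 9.1, give every Safety Population subject an ED time: EDs to the first result of at least 0.6 BU, or EDs to the last negative inhibitor test, marked as censored. State that unscheduled samples count; SAP 7.1 keeps unscheduled data out of summary tables, and SAP 9.1 makes an exception only for the shift summary.

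Replace Tables 14.2.1.5 and 14.2.1.6 with:

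- (a) subjects with an inhibitor, x/n, with an exact 95% interval;
- (b) inhibitor events over total EDs at risk, per 1,000 EDs, with an exact Poisson 95% interval;
- a listing of ED at detection for any case.

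The intervals are essential. Without them, a zero-case result would print only as a zero rate and add little to the visit tables. A cumulative-incidence curve is optional, since onset is known only to within the gap between tests.

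The cost is SAP wording and one re-programmed table. EDs and sample dates are already collected. The downside is a visibly wide interval, which is what 10 to 12 subjects support.
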